#### **2.1.4 Safety endpoints**

The safety analysis will be based on the reported adverse events and other safety information, such as clinical laboratory data, vital signs, ECG.

##### ***Observation period***

The observation period will be divided into 3 periods: pre-treatment, on-treatment and post-treatment.

- The **pre-treatment period** is defined as the time from when the patients give informed consent and the start of isatuximab.
- The **on-treatment period** is defined as the time from the first dose of isatuximab up to 30 days after the last dose of isatuximab.
- The **post-treatment period** is defined as the time from 31 days after the last dose of isatuximab to the study closure.

##### ***2.1.4.1 Adverse events variables***

Adverse events occurring from signature of informed consent form up to 30 days after the last isatuximab administration were to be recorded in the eCRF.

All isatuximab related AEs and SAEs ongoing at time of study treatment discontinuation were to be followed during the follow-up period until resolution or stabilization.

All AEs (including SAEs) will be coded to a lower-level term (LLT), preferred term (PT), high-level term (HLT), high-level group term (HLGT), and associated primary system organ class (SOC) using the version of MedDRA in effect at Sanofi at the time of database lock.

The severity of AEs was assessed according to NCI-CTCAE version 4.03.

##### ***Adverse event observation period***

- Pre-treatment adverse events are adverse events that developed or worsened or became serious during pre-treatment period
- Treatment-emergent adverse events are adverse events that developed or worsened or became serious during the on-treatment period

- Post-treatment adverse events are adverse events that developed or worsened or became serious during the post-treatment period

### ***Other significant adverse events***

Other significant adverse events will include adverse events of special interest (AESIs), respiratory AEs, and specific hematological analyses.

#### *Adverse events of special interest*

The following AEs are considered adverse events of special interest:

- Acute infusion associated reactions (IARs)
- Symptomatic overdose
- Pregnancy occurring in a female patient or in a female partner of a male patient

#### *Infusion associated reactions*

Infusion associated reactions, commonly observed with monoclonal antibodies, include AEs with onset date typically within 24 hours from the start of each isatuximab infusion (See Section 6.6 of the protocol for guidelines for IARs management). As described above, IARs are considered to be AESI.

Two analyses of IARs will be performed. The first one will be based on the investigator's reporting of IARs (i.e., as AESIs). For each IAR-AESI, the sites were instructed to report a generic term (infusion related reaction) and each individual symptom. For IAR analyses based on the generic term, a customized MedDRA query (CMQ) including the single preferred term of infusion related reaction will be used.

The second analysis of IAR will include TEAEs occurring within 24 hours (one table including causally related TEAEs, one table including all TEAEs regardless of causal relationship) from the start of each isatuximab infusion (i.e., TEAEs with onset on the same calendar day of the isatuximab infusion or on the following day).

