6.6.1 Management of Potential Infusion Associated Reactions (IARs)

Patient(s) should routinely receive pre-medications prior to isatuximab infusion as detailed in [Section 8.3](#) to reduce the risk and severity of IARs commonly observed with monoclonal antibodies. Infusion associated reactions (NCI-CTCAE, version 4.03 term Infusion related reaction), including “allergic/hypersensitivity reactions”, or “cytokine release syndrome/acute infusion reaction”, are defined as AEs related to isatuximab with onset typically within 24 hours from the start of the infusion.

Refer to [Appendix G](#) for diagnoses [Table 12](#) and symptoms typical of an infusion associated reaction [Table 13](#).

General guidelines for the management of IARs are provided in [Table 3](#).

Table 3 - Infusion associated reactions management

NCI CTCAE v. 4.03 criteria definition	Recommendation
Mild Grade 1 Infusion interruption not indicated; intervention not indicated	Continuation of isatuximab infusion is per the judgment of the Investigator following close direct monitoring of the patient's clinical status. Isatuximab infusion may be stopped at any time if deemed necessary. (If stopped, IAR will be classified as a Grade 2 as per NCI-CTCAE)
Moderate Grade 2 Therapy or infusion interruption indicated but responds promptly to symptomatic treatment (eg, antihistamines, NSAIDs, narcotics, IV fluids); prophylactic medications indicated for <=24 hrs.)	Stop isatuximab infusion; Give additional pre-medication with diphenhydramine 25 mg IV (or equivalent) and/ or IV methylprednisolone 100 mg (or equivalent) as needed. Isatuximab may be resumed ^a only after patient recovery, with slower infusion rate and with close monitoring. (ie. infusion may be restarted at one half of the original infusion rates. If symptoms do not recur after 30 minutes, the infusion rate may be increased in 50 mg/hour increments every 30 minutes, to a maximum of 400 mg/hour). Important: Additional blood sampling during the AE is required for analysis of markers of potential TLS (uric acid, lactate dehydrogenase [LDH], BUN, creatinine, potassium, phosphate, ionized or corrected calcium).

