10.5.5 Adverse Event of Special Interest

An AESI is an AE (serious or non-serious) of scientific and medical concern specific to isatuximab, for which ongoing monitoring and immediate notification by the Investigator to the Sponsor is required. Such events may require further investigation in order to characterize and understand them. Adverse events of special interest may be added or removed during a study by protocol amendment.

The following adverse events are considered AESIs:

- Acute infusion associated reactions (IARs; see [Appendix G](#) for diagnoses and symptoms typical of an IAR). An IAR is a related adverse event with onset within 24 hours from the start of the infusion. As defined in [Section 10.5.1](#), a main diagnosis and individual symptoms should be reported in the e-CRF. However, only the main diagnosis will be reported as AESI.

- During Phase I part, all protocol-defined potential or IMP related DLTs (as defined in [Section 9.1.1](#)) are considered AESIs, and as such, the Investigators will be required to report them to the Sponsor within 24 hours of the Investigator becoming aware of the adverse event. The Investigator will attach the DLT-specific CRF page to the DLT/AESI form.

Pregnancy occurring in a female patient entered in the clinical trial or in a female partner of a male patient entered in the clinical trial. It will be qualified as an SAE only if it fulfills one of the seriousness criteria (see [Section 10.4](#)).

- Symptomatic overdose (serious or non-serious) with IMP
An overdose (accidental or intentional) with the IMP is an event suspected by the Investigator.

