Appendix G Definitions of Infusion Associated Reactions (IARs)

Table 12 - Types of infusion associated reactions^a

Anaphylaxis
Acute coronary syndrome
Cytokine release syndrome
Drug hypersensitivity
Infusion related reaction

^a This list is not intended to be exhaustive

Table 13 - Symptoms typically associated with infusion associated reactions^a

Abdominal pain	Head discomfort	Pyrexia
Apnoea	Hoarseness	Respiratory distress
Bronchospasm	Hot flush	Rhinitis
Chest discomfort	Hypertensive crisis	Rhinorrhoea
Chest tightness	Hypoxia	Stridor
Chills	Influenza like illness	Tachycardia
Cough	Injection site pain	Throat irritation
Dizziness	Lacrimation increased	Tracheal stenosis
Dysgeusia	Laryngospasm	Tremor
Dyspnea	Myalgia	Urticaria
Feeling hot	Nasal congestion	Vision blurred
Flushing	Nausea	Vomiting
Headache	Pruritus	Wheezing

^a This list is not intended to be exhaustive

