***Deaths, serious adverse events, adverse events leading to withdrawal, and other significant adverse events***

- Death: see [Section 2.4.5.2](#).
- Serious adverse events
  - All serious TEAEs by PT presented by all grades and grade $\geq 3$ .
  - All serious TEAEs by primary SOC and PT, showing the number (%) of patients with at least 1 treatment-emergent adverse event.
  - All drug-related serious TEAEs related to isatuximab, by primary SOC and PT, showing the number (%) of patients with at least 1 treatment-emergent adverse event.
  - Listing of serious AEs.
- TEAEs leading to treatment discontinuation
  - Summary of TEAEs leading to treatment discontinuation by SOC and PT. If the number of patients who discontinued treatment due to a TEAE is  $\leq 5$ , no summary table will be provided. Instead, listing(s) will be provided.

Other significant adverse events, including IARs, respiratory TEAEs, hematological adverse events, TEAE leading to dose modification, other AESI, pre- and post-treatment AE).

- IAR-AESI (using the CMQ corresponding to the generic term of infusion related reaction reported by investigator as an AESI):
  - Analysis by patient: number of patients (used as denominator), worst grade by patient, number of episodes by patient (only 1 episode,  $\geq 1$  episode,  $\geq 2$  episodes, .... - an episode corresponds to a unique AE reference ID), first occurrence of IARs, patients with IAR at the first and/or subsequent isatuximab infusion, and number (%) of patients with at least 2 episodes of IARs at the same infusion.
  - Analysis by infusion: number of infusions (used as denominator), worst grade by infusion (a patient can have several IAR episodes at the same infusion).
  - Analysis by episode: number of episode (used as denominator), proportion of IARs occurring at each infusion, IAR duration, and day of onset.
- IAR-AESI including symptoms as reported by investigator
  - Summary of IAR-AESI by SOC and PT,
  - Listing of IAR-AESI
- Respiratory TEAEs:

- Lower respiratory TEAEs analyzed by IAR status (IAR or Non-IAR).
- Respiratory infection TEAEs analyzed by IAR status (IAR or Non-IAR).

In addition, late respiratory adverse events (i.e., occurring, worsening or becoming serious more than 30 days after last dose) will be analyzed as part of the post-treatment AEs analysis.

- Hematological abnormalities (including analysis of both AE and laboratory neutropenia):

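### The by-patient, by-infusion and by-episode infusion-reaction tables search one preferred term, so they can miss reactions recorded under another diagnosis that the protocol allows

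*SAP*

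**What the plan says.** Both SAPs (section 2.1.4.1, Infusion associated reactions) plan two analyses of IARs.

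- **First analysis.** It rests on the investigator's reporting of IARs as AESIs. The SAPs say that for each one "the sites were instructed to report a generic term (infusion related reaction) and each individual symptom", and that for analyses based on the generic term "a customized MedDRA query (CMQ) including the single preferred term of infusion related reaction will be used". Section 2.4.5.1 of both SAPs then lists analyses by patient, by infusion and by episode under "IAR-AESI (using the CMQ corresponding to the generic term of infusion related reaction reported by investigator as an AESI". These carry worst grade, number of episodes, first occurrence, infusion number, duration and day of onset.
- **Second analysis.** "The second analysis of IAR will include TEAEs occurring within 24 hours" of each infusion start, in one table limited to causally related events and one regardless of relationship. It does not depend on the preferred term.

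The protocol describes site reporting differently. Section 10.5.5 says that "a main diagnosis and individual symptoms should be reported in the e-CRF. However, only the main diagnosis will be reported as AESI", and points to Appendix G for the diagnoses. Table 12 there, headed "Types of infusion associated reactions", lists five: anaphylaxis, acute coronary syndrome, cytokine release syndrome, drug hypersensitivity and infusion related reaction. It adds that the list is not exhaustive.

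**The concern.** The SAP query is built for one reporting instruction (always record the generic term). Protocol 10.5.5 gives another (record a main diagnosis, with several to choose from). A site that follows 10.5.5 and enters anaphylaxis or cytokine release syndrome as the main diagnosis has complied with the protocol. Yet it has created an IAR-AESI that a query holding only infusion related reaction cannot find.

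The query-based tables are the only planned displays that describe IARs by number of episodes, first occurrence, infusion number and duration. An event missing from them is missing from the detailed description of an AESI. Reaction counts are also at risk of disagreeing between displays, because several of them refer to IARs without saying which definition applies.

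**Working it through.** No figure in the plan depends on this point, so there is nothing to reproduce. The check is a comparison of texts, followed by a small illustration.

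**Step 1. Do the two reporting rules agree?**

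| Source | What the site records as the IAR-AESI |
|---|---|
| Protocol 10.5.5 | A main diagnosis; only that diagnosis is the AESI |
| Protocol Appendix G, Table 12 | Five diagnoses, list not exhaustive |
| Protocol 6.6.1 | "Infusion associated reactions (NCI-CTCAE, version 4.03 term Infusion related reaction", described as including allergic or hypersensitivity reactions and cytokine release syndrome; then refers to Appendix G for diagnoses |
| SAP 2.1.4.1 (both phases) | The generic term infusion related reaction, plus each symptom |

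They do not agree. Section 6.6.1 leans towards the generic term. Section 10.5.5 and Appendix G do not require it.

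**Step 2. Where would an IAR recorded only as, say, anaphylaxis appear?**

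| Planned display | Included? |
|---|---|
| Query-based by-patient, by-infusion and by-episode tables (2.4.5.1, both SAPs) | No |
| Overview rows for IAR and Grade 3-5 IAR (both SAPs) | Not determinable: term set not stated |
| IAR versus non-IAR split of respiratory events (Phase 2 SAP) | Not determinable: IAR definition not stated |
| 24-hour tables (2.1.4.1, both SAPs) | Yes, if onset is on the infusion day or the next day |
| IAR-AESI summary by SOC and PT, and listing, as reported by the investigator (both SAPs) | Yes |
| Overview rows for AESI and Grade 3-5 AESI (Phase 2 SAP only) | Yes |

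The Phase 1 overview has no AESI rows, so the last line gives no cover there. The 24-hour tables are defined in 2.1.4.1 but are not repeated among the displays in 2.4.5.1.

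**Step 3. How large could the gap be?**

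The documents do not say how many IARs would carry another diagnosis alone, so any number is an assumption. The denominator is the Phase II safety set, about 30 patients (protocol summary, total expected number of patients). The 33-36 in protocol 13.1 is the efficacy sample pooled with Phase I. Protocol 13.4 reports the phases separately except for efficacy.

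- One missed patient: 1/30 = 3.3 percentage points.
- For scale, protocol Table 1 shows infusion related reaction in 13/25 = 52% at 20 mg/kg QW/Q2W in the earlier study. Applied to 30 patients, 0.52 × 30 = 15.6, or about 16.

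| Patients with only another main diagnosis (assumed) | Query-based IAR rate |
|---|---|
| 0 | 16/30 = 53.3% |
| 1 | 15/30 = 50.0% |
| 2 | 14/30 = 46.7% |
| 3 | 13/30 = 43.3% |

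The first row is what results if sites always added the generic term.

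**The case against.** The best defence is that nothing is lost in practice. Both SAPs state, in the past tense, that sites were told to record the generic term for every IAR-AESI, and protocol 6.6.1 names that same term as the CTCAE label. The site instructions themselves are not among the documents. If they were followed, the single-term query finds every IAR. This stands as a condition on the size of the problem. It does not remove the mismatch with 10.5.5, because the protocol text alone does not secure the generic term.

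A second defence is that the plan has other routes to these events. This also stands, and it limits the point. A reader might infer that anaphylaxis or cytokine release syndrome would vanish from all IAR reporting. The documents do not support that:

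- The causally related 24-hour table closely matches the protocol's own definition of an IAR (related, with onset within 24 hours of infusion start).
- The IAR-AESI summary and listing would show the event by name.
- In Phase 2 the only AESIs are IARs, symptomatic overdose and pregnancy, so the Grade 3-5 AESI row would count a severe one.

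These routes do not replace the query-based tables. The 24-hour tables are not confined to reactions that the investigator called IARs. The SOC and PT summary mixes diagnoses with symptoms and states no episode breakdown.

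A reader might also infer that the loss is selective, so that the Grade 3-5 IAR rate is biased downward. That is not shown. No passage says that sites use other terms for severe reactions. Protocol Table 1 records 2/24 (8.3%) Grade 3 or higher events at 10 mg/kg Q2W under exactly the generic term. Cytokine release syndrome and drug hypersensitivity are not severe by definition.

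**Conclusion.** The point holds in a limited form. The query-based IAR-AESI tables in both SAPs can miss a reaction whose only recorded diagnosis is another Appendix G term, and the overview IAR rows may miss it too. Protocol 10.5.5 permits such a record, and the SAPs assume it does not occur.

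The loss is zero if sites always also recorded the generic term. Otherwise neither its size nor its direction by severity can be derived from the documents. The 3.3 percentage points per missed patient is an illustration that assumes about 30 patients in the Phase II safety set. The analyses are descriptive, with no test or decision rule attached, so what is at stake is the accuracy and consistency of the safety description. The single-term query is the first of two IAR analyses, and nothing in the SAPs ranks it above the second. The change is still worth making, because it closes a gap in a stated selection rule with data already collected.

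**What to change.** In section 2.1.4.1 of both SAPs, base the by-patient, by-infusion and by-episode tables on the investigator's IAR-AESI report (main diagnosis), whatever its preferred term. Alternatively, extend the query to all Appendix G diagnoses that are reported as IAR-AESI.

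State that the same definition governs the overview rows for IAR and Grade 3-5 IAR in both SAPs, and the IAR versus non-IAR split of respiratory events in the Phase 2 SAP. Reconcile protocol 10.5.5 with the SAP account of what sites were told to record.

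The cost is a change of wording and one selection step in the program, with no new data. The reported IAR rate may rise slightly.

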#### *Respiratory AEs*

Analysis of respiratory TEAEs will focus particularly on the groupings by CMQ.

The respiratory AEs with onset during the post-treatment period will be analyzed separately, according to the same methods above.

#### *Hematological analyses (including both AE and laboratory neutropenia)*

Neutropenia (from laboratory abnormalities) will be displayed along with neutropenic complications (e.g., neutropenic infections, febrile neutropenia).

#### **2.1.4.2 Deaths**

The deaths observation period are per the observation periods defined in [Section 2.1.4](#).

- Death on-treatment: deaths occurring during the on-treatment period
- Death post-treatment: deaths occurring during the post-treatment period

#### **2.1.4.3 Laboratory safety variables**

Clinical laboratory data consists of blood analysis, including hematology, clinical chemistry, and urinalysis. Clinical laboratory values after conversion will be analyzed into standard international units and international units will be used in all listings and tables.

Blood samples for clinical laboratories will be taken as defined in the study flow charts and as clinically indicated. The laboratory parameters will be classified as follows:

- Hematology
  - **Red blood cells, platelets and coagulation:** hemoglobin, hematocrit, mean corpuscular volume, red blood cell count, platelet count, prothrombin time (expressed as international normalized ratio), activated partial thromboplastin time
  - **White blood cells:** white blood cell count, neutrophils, lymphocytes, monocytes, basophils, eosinophils
- Clinical chemistry
  - **Metabolism:** glucose, total protein, albumin
  - **Electrolytes:** sodium, potassium, chloride, calcium, corrected serum calcium, phosphate, magnesium
  - **Renal function:** creatinine, blood urea nitrogen, uric acid, e-GFR (revised equations for e-GFR in Japanese)
  - **Liver parameters:** alanine aminotransferase, aspartate aminotransferase, alkaline phosphatase, lactate dehydrogenase, total and conjugated (direct) bilirubin
  - **Pregnancy test:** serum  $\beta$ -human chorionic gonadotropin (all female patients)
  - **Hepatitis screen:** hepatitis B surface antigen (HBs-Ag, HBc-Ab and HBs-Ab), HBV-DNA, anti-hepatitis-C antibody (HCV-Ab)

Urine samples will be collected as follows:

- **Urinalysis** – quantitative: pH and specific gravity
- **Urinalysis** – qualitative: blood, ketones, bilirubin, leucocytes, nitrites, proteins and glucose

Technical formulas are described in [Section 2.5.1](#).

#### **2.1.4.4 Vital signs variables**

Vital signs include: heart rate, respiratory rate, temperature, body weight, and systolic/diastolic blood pressure.

#### **2.1.4.5 Electrocardiogram variables**

Electrocardiogram variable include: 12 leads electrocardiogram and 2-D echocardiogram or MUGA scan. ECG was to be performed at screening and if clinically indicated.

#### **2.1.4.6 Other safety endpoints**

Other safety endpoints include:

- Cytokines
  - TNF- $\alpha$ , IL-4, IL-6, IL-1- $\beta$ , IFN- $\gamma$
- IAR laboratory test
  - Complement (C3a, C4, CH50)
  - Serum tryptase
- Chest X-ray at baseline and as clinically indicated.
- Tumor lysis syndrome (TLS)

#### **2.1.5 Pharmacokinetic variables**

Isatuximab plasma concentrations will be summarized and the following PK individual parameters will be calculated:

- Cumulative AUC over a 1, 2 or 4 week interval (AUC1W, AUC2W, AUC4W)
- $C_{\text{trough}}$  (pre-dose concentration) at 1, 2, 4 weeks
- $C_{\text{max}}$  at Cycle 1 Day 1, Cycle 2 Day 1 and Cycle 4 Day 1
- Clearance (CL)
- Accumulation ratios (AUCss/AUC1W). AUCss is AUC at steady state.

#### **2.1.6 Immunogenicity**

Human ADA to isatuximab was assessed during the study as defined in the protocol.

##### ***Observation period***

The observation period will be divided into 2 periods: ADA pre-treatment and ADA on-study observation.

- ADA pre-treatment period: The ADA pre-treatment period is defined as the time from signed informed consent to the first isatuximab administration.
- ADA on-study observation period: the ADA on-study observation period is defined as the time from first isatuximab administration until Cycle 10.

Patients with at least one ADA result during the ADA on-study observation period will be considered evaluable for ADA.

***ADA attributes:***

- **Pre-existing ADA** is defined as ADA that was present in samples drawn during the ADA pretreatment period.
- **Treatment boosted ADA** is defined as preexisting ADA with an increase in titer value between pre-treatment and post-treatment samples of at least two titer steps during the ADA on-study observation period. With a 2-fold serial dilution, this means that the post-treatment sample titer value is at least ( $\geq$ ) 4 fold of pretreatment titer value.
- **Treatment-induced ADA** is defined as ADA that developed at any time during the ADA on-study observation period in patients without pre-existing ADA, including patients without pretreatment samples.
- **Transient ADA response** is defined by:
  - Treatment induced ADA detected only at one sampling time point during the ADA on study observation period (excluding the last sampling time point), OR
  - Treatment induced ADA detected at two or more sampling time points during ADA on-study observation period, where the first and last ADA-positive samples (irrespective of any negative samples in between) are separated by a period less than 16 weeks, and the patient's last sampling time point is ADA negative.
- **A persistent ADA response** is defined by:
  - Treatment induced ADA detected at two or more sampling time points during the ADA on-study observation period, where the first and last ADA-positive on study samples are separated by at least 16 weeks (irrespective of any negative samples in between), OR
  - Treatment induced ADA detected in the last two sampling time points (both are positive), irrespective of the time period in between.
  - Indeterminate ADA is defined by treatment induced ADA detected only at the last sampling time point with all previous samples being negative

